Title: Efficacy of the Quell Wearable Device for Treatment of Central Sensitization-related Pain Among Persons with Chronic Overlapping Pain Conditions

NCT #: 05540002

Date: 09/07/2022

RESEARCH DESIGN AND METHODS

We will recruit 115 patients (see power analysis) with a presentation of multiple COPCs and randomize each of the subjects to one of two treatment conditions: 1) the standard Quell device, and 2) a Sham Quell device (control). All participants will be adults age 21 or older with multiple chronic pain conditions and QST-assessed evidence of sensory hypersensitivity. Patients will be invited to participate if they own a smartphone (iPhone or Android device) and can download the pain app and the Quell Relief mobile app onto their device. Individuals who are interested in the study and who do not own a smartphone will be supplied a temporary study-specific tablet to monitor their daily progress and to control their Quell device. Patients will be included if they (1) have chronic pain related to multiple chronic pain diagnoses (headaches, joint pain, back pain, or any of the other COPCs) for > 3 months' duration, (2) average 4 or greater on a pain intensity scale of 0 to 10, and (3) are able to speak and understand English. We will supply access to a Spanish version of the study pain app for those who are more comfortable responding in Spanish, but some English proficiency will be required. Subjects will need to meet the criteria outlined by Maixner and others (2016), for COPC to be considered for inclusion in this trial: (1) multiple pain sites and two or more pain diagnoses, (2) pain for 3 months or longer, (3) pain that is not accounted for by any other progressive disease (e.g., cancer, MS), and (4) meet hypersensitivity cutoffs based on QST (described below). (5) We will also require that the participants have a "physician diagnosis" of the pain conditions, meaning that they have been told that they have chronic overlapping pain conditions and their diagnoses have been entered in a medical record by a healthcare provider.

Patients will be excluded from participation if they meet any of the following criteria: (1) diagnosis of cancer or any other malignant disease, (2) acute osteomyelitis or acute bone disease, (3) present or past DSM-V diagnosis of schizophrenia, delusional disorder, psychotic disorder, or dissociative disorder that would be judged to interfere with study participation, (4) pregnancy, (5) any clinically unstable systemic illness judged to interfere with treatment, (6) a pain condition requiring urgent surgery, (7) an active substance use disorder, such as cocaine or IV heroin use (positive on the Mini International Neuropsychiatric Interview; M.I.N.I. v.5.0), that would interfere with study participation, and (8) have an implanted cardiac pacemaker, defibrillator, or other implanted device. All subjects will be asked to not change their treatment during the study period, (9) Raynaud's syndrome, or (10) Open cuts/sores.

Patients will be equally randomized to one of two experimental groups in this trial (i.e., Active Quell or Sham Quell) with the goal of having 50 subjects complete the trial in each group. The Sham Quell will look exactly like the Active Quell but will be programmed to give 2 minutes of stimulation three times during the 1-hour therapy session (2 minutes of stimulation at 0, 28, and 58 minutes, etc.). Subjects will be told that they will be exposed to two treatment conditions, lower intensity or higher intensity stimulation, and will be asked to use the device (standard or sham) every day for 12 weeks. Neither the investigators nor the study participants will know for sure which device they will be receiving. All subjects will complete assessment measures and be followed for 3 months. Recruitment will not be

restricted based on race or ethnicity. Efforts will be made to recruit at least 15% minorities. Since COPCs are identified more often among women than men, we will actively recruit at least 25% males. All participants will get assistance in downloading both the pain app and Quell Relief mobile app and have access to a research assistant (RA) who will answer any questions and help manage any problems that the individual may encounter. All participants will also be given a more extensive battery of QST testing at baseline and again at the end of the study. We will use an enriched design by first having the potential subjects try the Quell device. We anticipate that very few potential study participants will decide not to participate in a trial because they dislike the feeling of the Quell based on the results of previous trials. If they find that they would be willing to use the device they will be included in the study. If they dislike using the device on an initial trial, their age, gender, ethnicity and pain duration will be noted and the participants will be thanked for their interest in the study and dismissed.

All subjects (Quell and Sham Quell condition) will be encouraged to use their assigned device for at least 3 therapy sessions (3 hours of stimulation) every day, and to wear the device as often as possible, including while sleeping. Tracking of use of the device will be available electronically through the Quell Relief mobile app (subject data will be de-identified on the Quell server). All demographic and daily pain assessment data will be stored on a secure server (Mass General Brigham Amazon Web Server - MGB AWS) using the Veracode-tested study pain app and portal. Messages will be sent via the 2-way messaging pain app program to help track use of the device and to monitor and encourage active participation. Subjects will be instructed to enter daily assessments only when they are wearing the Quell device. Patients who wish to discontinue the study will be allowed to do so at their request. If the participant is willing, we will meet with her or him to understand reasons for discontinuing the study and problem-solve to see if there would be a way to keep following the individual. All subjects will be asked to complete a packet of questionnaires at the conclusion of the first 6-week study phase and then at the 3-month mark. All subjects will also be asked to participate in the full QST session described below at baseline, and then again at the end of the study (i.e., QST will be completed at the same poststudy visit when outcome measures are collected). Each subject will be compensated \$50 at baseline, \$25 mid study, and \$100 at study completion upon receipt of their completed questionnaires for a possible total of \$175. At the end of the study subjects will be informed which device was the standard Quell device and they will be encouraged to keep this device for future use. Those in the Sham treatment arm will be offered a standard Quell for use after the study. It is expected that 15% of the subjects will dropout before completing the trial and recruitment of a total of 115 subjects may likely be needed to successfully complete the study.

Quantitative Sensory Testing (QST) Protocol: All subjects will be administered a battery of sensory assessment measures at baseline and again at the end of the 3-month study. A list of the QST measurements used in this proposed study is presented in Table 2. We will assess mechanical pain assessment and cold pain assessment. For mechanical pain, responses to punctate mechanical stimuli will be measured using a standard set of weighted probes (pinprick stimulators) that provides estimates of pain threshold and mechanical temporal summation. Singular taps will be performed on the metacarpophalangeal joint of the middle finger of the non-dominant hand using these probes (*Touch-Test Sensory Evaluator; www.ncmedical.com*) developed by the German Research Network (Backonja, 2009). The lowest-force stimulator that produces a sensation of discomfort at the level 10 out of a 100-point scale will then be used to assess the temporal summation of pain that occurs with rapid administration of identical stimuli for a series of 10 pinpricks (with 1-second inter-stimulus intervals). Participants will be asked to rate the painfulness of the first, fifth, and tenth stimulus; mechanical temporal summation will be defined as the increase in pain from the first to the final stimulus. A Somedic pressure algometer will be utilized to assess responses to pressure stimulation at several

anatomical sites. Pain pressure thresholds (PPT) will be determined twice on the right and left sides of the body: the trapezius, and thumb joint. Mechanical pressure will be applied using a 0.5-cm² probe covered with 1mm polypropylene pressure-transducing material; pressure will be increased at a steady rate of 30 kPA/s until the subject indicates that the pressure is painful. Finally, we will use cuff algometry to assess responses to sustained mechanical pressure. A Hokanson rapid cuff inflator will be used to inflate a standard blood pressure cuff around the gastrocnemius muscle of the dominant leg until the subject indicates a pain level was 40 out of a 100-point scale. This pressure will be used in the next test and will not be changed. Over the course of 2 minutes, at 30 second intervals, the subject will be asked to rate her or his current pain level on a scale 0 to 100. As with each of these psychophysical testing procedures, participants will be informed that they could terminate the procedure at any time.

For cold pain assessment, responses to noxious cold will be evaluated using a repeated cold pressor task (CPT), which involves immersion of the right hand in a circulating water bath (Neslab RTE17) maintained at a temperature of 4°C. The CPT is the most commonly used method of pain induction in the laboratory and has demonstrated clinical relevance. Participants will undergo a series of several cold pressor tasks, with the first 2 consisting of serial immersions of the dominant hand for 15 seconds, with 2 minutes between immersions. Once the subject removes their hand, pain ratings will be asked at 0 seconds, 15 seconds, 30 seconds, and 60 seconds. If the subject is not able to remain in the water for the full 15 seconds, they will be able to remove it at their discretion with the same post-water intervals. Conditioned Pain Modulation (CPM, which refers to the phenomenon of one noxious stimulus inhibiting the pain of a second noxious stimulus) will be measured during these cold pressor trials by assessing PPTh during the immersion. The final CPT will involve an immersion of the dominant hand lasting until a participant reached maximum pain tolerance (or a 3 min maximum). Their pain level will be asked in 15 second intervals while submerged and as soon as they removed the hand from the water. The participants will rate the intensity of the cold pain on a 0-100 scale ("no pain" to "most intense pain imaginable"). These procedures are similar to those we have utilized in prior studies of patients with OA and other chronic pain conditions (Jamison, 2018, 2019; Edwards, Wasan, 2011; Edwards, 2016). After 30% of the proposed sample has been enrolled, a blinded observer will assess the QST screening data to ensure that the proposed cutoffs are not excluding a problematically high percentage of interested participants.

Blinding: The proposed randomization ratio will be 1:1 Active to Sham device. The Sham device is identical to the Active Quell in all aspects with one exception. While the Active Quell typically delivers 1 hour of continuous stimulation during a therapy session, the Sham Quell device will deliver only three 2minute periods of stimulation (at 0, 28 and 58 minutes) within each 60-minute therapeutic session. Recent studies suggests that this limited stimulation offers some perceived analgesic effect (Jamison, Edwards et al., 2021; Jamison, Curran et al., 2021). The subjects will be informed that they will be receiving either low or high intensity therapy. Neither the principal investigator, the co-investigators, the research assistant (RA, who will serve as the study coordinator), nor the subjects will know if they are given a sham device or the actual Quell device. The devices will be randomly numbered and provided by NeuroMetrix and information about the device assignment will be managed through NeuroMetrix. At the end of 6 weeks and again after 3 months, subjects will be asked if they thought they had the Sham (low intensity) Quell or (high intensity) Active Quell device. The co-principal investigators and the RA will be asked to identify which subjects they thought had Active Quell vs the Sham Quell device prior to analyses of the data. Both the Active Quell and the Sham Quell will communicate via Bluetooth with the same mobile application. This application provides the subjects with a dashboard of device information, trending data on device usage, and sleep quality. This same information will be synced to a cloud database so that investigators involved in the study can collect these data remotely, as well as monitor

adherence with the device. In a past unpublished investigation when this blinding procedure was used among 17 subjects and 11 physicians, investigators accurately guessed the device (sham or active) a subject was randomized to in 11 of 17 participants (64.7%). Eleven of 17 (64.7%) study participants accurately guessed the device to which they were randomized. However, in a recent randomized study in which subjects were assigned to either an Active or Sham Quell device, most of the subjects (84.9%) believed that they had been assigned to the Sham Quell device (Jamison, Edwards et al., 2021; Jamison, Curran et al., 2021).

Patient Measures: Participants will complete measures recommended by the Initiative on Methods, Measures, and Pain Assessment in Clinical Trials (IMMPACT; Dworkin et al, 2005; Gewandter et al., 2021) as primary outcomes. We will be tracking the patients using validated measures of pain (The Brief Pain Inventory - BPI), coping (Pain Catastrophizing Scale - PCS), level of disability (Pain Disability Index -PDI), mood (Hospital Anxiety and Depression Scale - HADS), presence of neuropathic pain (Pain Detect Neuropathic Pain Questionnaire - painDETECT), pain symptoms and function (Symptom Impact Questionnaire - SIQR), impression of change (Patients' Global Impression of Change - PGIC), healthcare utilization (monthly clinic and ED visits), and overall satisfaction (Satisfaction and qualitative questions developed for this study specifically related to use of a pain management device; see Table 1). We will also track daily ratings of pain, sleep, activity interference, and mood through the pain app. Objective measures of activity, gait, and sleep will be collected by the devices. The 7-item activity interference scale of the Brief Pain Inventory will serve as the primary outcome.

Research Objectives: This study is expected to take 18-24 months to complete and is designed to gather information about the use of the Quell for persons with COPCs. We hypothesize that those using the Active Quell device will report reduced pain compared with the Sham Quell condition. We also expect that those using the active device will show improvement in sleep, mood, and level of activity over the 3-months of using the device. We hypothesize that frequency of using the Quell (increased tolerability and adherence) will be correlated with greater reduction in pain. We hypothesize that the device will be safe to use and will demonstrate a reduction in healthcare utilization (reduced clinic and ED visits). We will also investigate use of prescription opioids and other nonopioid pain medications among the study subjects and determine the effect of daily use of the Active Quell (vs. Sham Quell) on intake of prescription pain medication. Finally, based on preliminary analyses from prior Quell studies, we will investigate whether certain individuals report greater benefit from using the Active Quell than others and, in particular, we predict that those with more pain sensitivity and longer duration of pain will demonstrate most benefit from the Active Quell. The previous studies in LBP and fibromyalgia patients both yielded evidence that the most pain-sensitive patients reported the greatest reductions in pain with Active Quell use. In the present proposal, we will be recruiting participants with evidence of sensitization at baseline and we will evaluate whether the most-sensitized patients with COPCs, even within a generally sensitized group of patients, show the greatest analgesic benefits. We will examine trends from the daily pain ratings on the pain app since it gives multiple daily pain ratings over the course of the study. We will target the 7-item activity interference subscale of the BPI (0=does not interfere; 10=completely interferes) as the primary outcome, and the PCS, PDI, HADS, painDETECT, SIQR, PGIC, healthcare utilization, and satisfaction questions as secondary outcome measures.

Statistical POW

Power calculations, as outlined by Cohen (1988), were performed to determine the probability of detecting clinically significant differences between treatment conditions in the primary area of measurement. These calculations assumed a two-tailed test and alpha level of 0.05 confirming the

hypotheses that the Active Quell would be associated with general overall improvement in activity interference on the activity subscale of the Brief Pain Inventory. In our previous work (Jamison, Wan et al., 2019; Jamison, Curran et al., 2021; Jamison, Edwards et al., 2021), we had a high rate of consent to participate among recruited patients, with minimal attrition. We assessed power based on our preliminary data and previously published studies. The power analysis revealed that a sample size of 100 subjects (50 per treatment arm) using a 2-sample t-test for a difference in mean pre/post change score gives the study a >85% probability of detecting a 1.5-point group difference on a 0-10 rating scale (assuming a standard deviation of 1.8). Conventional metrics suggest that a 30% change or difference score is clinically meaningful (Dworkin et al., 2021), and this sample size would provide adequate power to detect a group difference of approximately 20%. Most of the analyses in the proposed study will involve delta scores reflecting changes within subjects (both uncorrected and adjusted - least squares, LS). We also will conduct multi-level modeling analyses of the daily pain assessments. We will examine the distribution of the delta scores between treatment arms and will ascertain whether that distribution is normal. This information will allow us to determine whether parametric (e.g., ANCOVA) or nonparametric analyses should be used. Collectively, this sample size (n=100 total), together with our previously observed very high retention rates and the substantial efficacy of the device, will provide more than adequate power to detect moderate-size effects.

Multivariate imputation with chained equations (MICE) will be used to fill in missing assessments (including for subjects that drop out). MICE is valid under the assumption that data is missing at random (MAR). Variables will be modeled using normal regression. For each efficacy measure, the imputation model will include the available baseline, week-6 and 3-month data, demographics (age, BMI, education) and pain characteristics. The active and sham groups will be separately imputed. The same random-number seed will be used for computation of 250 complete (i.e., no missing data) datasets for each efficacy measure. For each dataset, the 3-month least-square mean change scores will be determined. The results will then be combined according to Rubin's rule. A sensitivity analysis for data missing not at random (MNAR) rather than MAR will be performed using delta-based MI. Specifically, the LS mean change scores will be reanalyzed with deterministic increases to the 3-month assessments (i.e., smaller change scores) of subjects on active treatment that withdrew from the study.

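### Daily ratings are entered only while the device is worn, so the daily-pain analysis is sampled on post-randomisation device use and the missing-data plan does not cover the gap

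*Combined protocol and SAP*

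**What the plan says.** Research Design and Methods sets the entry rule for both arms: "Subjects will be instructed to enter daily assessments only when they are wearing the Quell device". The same paragraph encourages at least three therapy sessions daily and asks subjects "to wear the device as often as possible, including while sleeping". It adds: "Tracking of use of the device will be available electronically through the Quell Relief mobile app".

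Patient Measures shows what the rule covers: "We will also track daily ratings of pain, sleep, activity interference, and mood through the pain app". Research Objectives says "We will examine trends from the daily pain ratings on the pain app", and the statistical section adds "We also will conduct multi-level modeling analyses of the daily pain assessments". It gives no model terms, contrast, adjustment for wear or missing-data assumption for these models. Research Objectives also states: "We hypothesize that frequency of using the Quell (increased tolerability and adherence) will be correlated with greater reduction in pain".

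The closing paragraph of the statistical section handles missing data by chained-equations imputation under missing at random. Its specification is visit-based: "For each efficacy measure, the imputation model will include the available baseline, week-6 and 3-month data", together with demographics and pain characteristics. The result is the 3-month least-squares mean change, and the not-at-random sensitivity analysis shifts the 3-month values of active-arm withdrawals. Neither daily ratings nor device use is mentioned.

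**The concern.** Whether a daily rating exists depends on wearing the device, which the subject decides after randomisation. Three consequences follow.

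- **The comparison changes.** The data describe pain while worn on active against pain while worn on sham, not pain under assignment to each device. This follows from the instruction itself and needs no assumption about behaviour.
- **Bias is possible.** If wear depends on that day's pain differently in the two arms, a false difference can appear or a true one can be hidden. The arms deliver different amounts of stimulation, so different wear behaviour is plausible. The documents do not show that it occurs.
- **An effect present only during wear is overstated** when it is read as an effect over all days.

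The hypothesis linking frequency of use to pain reduction has a related problem. If it is tested with the daily ratings, use is the exposure and also decides which outcomes are recorded.

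**Working it through.** **The plan's own figure.** The documents give no figure for the daily analysis. Their only power statement concerns the primary outcome: 50 per arm, 1.5 points, SD 1.8, two-sided 0.05, power above 85%. A two-sample t-test with these inputs has 98.5% power, so the stated bound is met. The present point does not touch that figure.

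**Reach of the safeguards.** The imputation inputs, the imputed quantity and the sensitivity shift all belong to scheduled visits. A subject who remains in the study with the device off is not a withdrawal, and unworn days are not visit assessments. Neither is covered.

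**Illustrative bias, no true effect.** All inputs here are assumptions:
- within-person daily deviation e ~ N(0, SD), SD 1.2 to 1.5
- P(wear) = logit⁻¹(logit(w) + b·e), where w is the wear probability on a day of average pain
- b = 0.3 per pain point in size

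The bias is the arm difference in mean e among worn days. By numerical integration, in points:

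| w | SD | slope in one arm only | opposite slopes (+0.3, −0.3) |
|---|---|---|---|
| 0.7 | 1.2 | 0.128 | 0.257 |
| 0.7 | 1.5 | 0.199 | 0.399 |
| 0.8 | 1.2 | 0.087 | 0.174 |
| 0.8 | 1.5 | 0.137 | 0.273 |
| 0.9 | 1.2 | 0.045 | 0.089 |
| 0.9 | 1.5 | 0.071 | 0.142 |

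Equal slopes in both arms give 0. As a hand check, the one-arm bias is close to b·SD²·(1−w). For w = 0.7 and SD 1.2 this is 0.3 × 1.44 × 0.3 = 0.130; for SD 1.5 it is 0.3 × 2.25 × 0.3 = 0.203.

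**False rejection at nominal 5%.** Further assumptions: 50 per arm, 84 days (12 weeks), one rating per worn day, between-person SD 1.5, random-intercept analysis with variances taken as known, 3,000 simulated trials per setting.

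| w | slopes | SD 1.2 | SD 1.5 |
|---|---|---|---|
| 0.7 | one arm | 7.0% | 10.5% |
| 0.7 | opposite | 13.6% | 27.2% |
| 0.9 | one arm | 5.9% | 5.2% |
| 0.9 | opposite | 5.9% | 7.8% |

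Equal slopes give 4.6-5.1%.

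Hand check for w = 0.7, SD 1.5: worn days = 84 × 0.7 = 58.8. The standard error of the arm difference is √[2 × (1.5² + 1.5²/58.8)/50] = 0.303. A bias of 0.199 is 0.66 standard errors, which gives about 10% rejection; 0.399 is 1.32 standard errors, which gives about 26%.

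A separate simulation compared person means (both SDs 1.5, wear about 70%) and let wear depend on the subject's overall pain level as well as the daily deviation. With slopes of 0.3 it gave 0.20 points and 10% rejection (one arm), and 0.36 points and 23% (opposite). The sign of the bias followed the sign of the slope.

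**Effect present only on worn days.** If the worn-day difference is d, the all-day difference is w·d. With d = 1.0 this is 0.7, 0.8 and 0.9 points at w = 0.7, 0.8 and 0.9.

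**The case against.** The strongest reply is that little depends on these data. The primary outcome is BPI interference, daily ratings are in neither the primary nor the secondary list, and no between-arm daily contrast is written out. All of that stands. The contrast is implied by the hypothesis of reduced pain on active and by the planned multi-level models, and describing the daily analysis as supportive is this review's reading.

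The rule may also bite less than it seems. A subject who wears the device at any time in a day can still rate that day, use is encouraged through messages, and people who dislike the device are screened out beforehand. At an assumed 95% of days worn, the same integration gives only 0.02-0.04 points (one-arm slope) or 0.05-0.07 (opposite slopes), with rejection of about 5.1-5.7%. Nothing in the documents supports opposite slopes. These points limit the likely size but leave the gap open: no wear rate is given, and choosing when in the day to rate can itself be selective.

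A likelihood-based multi-level model does handle unbalanced daily data under missing at random. The plan does not state that assumption, and it fails if wear depends on that day's unrecorded pain.

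Finally, pain while wearing the device is a legitimate target, and labelling it with wear rates by arm would cure the interpretation. It would not provide the data for a comparison by assignment, because usage logs show when the device was worn and not the pain on unworn days.

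**Conclusion.** The concern holds and should be fixed, although it does not affect the primary outcome, its power or the sample size. It is certain that, followed as written, the instruction restricts the daily data to time on the device, that the plan does not say so, and that the specified missing-data methods do not reach the omitted days.

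Bias is a plausible risk and has not been shown. It requires a wear-pain relation that differs by arm, and it could favour either arm. Under the assumptions above it ranges from nothing (equal slopes) through 0.04-0.20 points (one-arm slope, 90% to 70% wear) to 0.09-0.40 points (opposite slopes). False rejection reaches 14-27% only when 70% wear and opposite slopes occur together; at 90% wear it is about 5-8%. Confidence is moderate, because the wear rates, daily SDs and slopes are all assumed.

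**What to change.** Replace the entry instruction in Research Design and Methods with: *Subjects will enter a daily rating every day at a fixed prompt, whether or not the device is being worn, and will record whether it is being worn.*

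In the statistical section, make the multi-level model of all daily ratings by assigned arm the main daily analysis and state its missing-data assumption. Keep the while-worn ratings as a labelled sensitivity analysis. Report days worn and days rated by arm.

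The cost is one changed instruction, one yes/no item in the pain app and a few lines of analysis text. The usage log and messaging system already exist. The downside is a small added burden: one extra item, and some reminders on days without device use. The change has to be made before ratings are collected.

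### As written, the week-6 blinding question labels low intensity as sham midway through treatment, before the self-reported 3-month primary outcome; neutral wording and a fixed order would remove the risk at almost no cost

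*Combined protocol and SAP*

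**What the plan says.** Two places set out what subjects hear about their treatment. Research Design and Methods states: "Subjects will be told that they will be exposed to two treatment conditions, lower intensity or higher intensity stimulation". The Blinding section repeats it: "The subjects will be informed that they will be receiving either low or high intensity therapy". Neither sentence mentions a sham.

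Disclosure comes later. In the procedures part of Research Design and Methods: "At the end of the study subjects will be informed which device was the standard Quell device".

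The guess is placed earlier than that. The Blinding section gives the timing, "At the end of 6 weeks and again after 3 months, subjects will be asked", and the content, "subjects will be asked if they thought they had the Sham (low intensity) Quell or (high intensity) Active Quell device". Subjects "will be asked to use the device (standard or sham) every day for 12 weeks", so the first guess falls at the midpoint.

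On the endpoint, Patient Measures states: "The 7-item activity interference scale of the Brief Pain Inventory will serve as the" primary outcome. The missing-data paragraph at the end of the plan analyses change to 3 months. Questionnaires are also collected at 6 weeks, daily app ratings run through the study, and QST is repeated at the final visit. The plan does not say whether the guess comes before or after the questionnaires at either time, and the statistical section names no analysis that uses the guesses.

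**The concern.** The blind relies partly on how the treatments are described. Both devices are presented as therapy that differs in intensity, so a subject who feels little stimulation can still believe that he or she is being treated. A question that couples low intensity with the word sham removes that reading for anyone who takes the words at face value. It does so while half of treatment is still ahead and before the primary outcome is measured.

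The primary outcome is the subject's own rating of interference on a 0-10 scale, so expectation can influence it directly. A change in belief could also affect device use, daily ratings or the decision to stay in the study during the last six weeks. If the guess precedes the week-6 questionnaires, those answers are exposed too, and week-6 data enter the imputation model for the 3-month result.

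**Working it through.** This is mainly a comparison of statements, with a little arithmetic.

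**1. Framing against question.** Subjects are told of lower or higher intensity (Research Design and Methods; Blinding). The guess as described (Blinding) offers sham or active, with the intensity terms in parentheses. The added information is that a sham exists and that it is the low-intensity device. A subject's own assignment is not added.

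**2. Timing.** Treatment lasts 12 weeks and the first guess is at week 6. Remaining treatment is (12 − 6)/12 = 50%. The primary assessment at 3 months comes after it. The planned disclosure comes at the end of the study, so the label reaches subjects about six weeks ahead of it.

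**3. Whether a subject could use the label.** The Blinding section gives the sham three 2-minute periods per 60-minute session: 3 × 2 = 6 minutes, and 6/60 = 10%. The active device typically stimulates continuously for the hour. The difference can be felt, so a subject has something to match to the label. The cue is present from the first day, with or without the question.

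**4. The plan's earlier blinding data.** In the unpublished investigation, 11 of 17 subjects guessed correctly: 11/17 = 64.7%, as stated. The exact 95% confidence interval is 38% to 86% (p = 0.33 against 50%). This neither shows nor excludes unblinding.

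**5. The later randomised study.** The plan reports that "most of the subjects (84.9%) believed that they had been assigned to the Sham Quell device". The figure is not split by arm. Assume 1:1 allocation in that study (the plan does not state it), and write *s* and *a* for the percentage believing sham in the sham and active arms:

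- (s + a)/2 = 84.9, so s + a = 169.8.
- If s = 100, then a = 69.8 and the excess in the sham arm is 100 − 69.8 = 30.2 points.
- If a = 100, then s = 69.8 and the excess is −30.2 points.

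The between-arm difference in sham belief in that study, from all causes together, therefore lay somewhere between about −30 and +30 points. Its sign is not known.

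**6. Size of bias.** A figure would need the share of subjects in each arm whose belief is moved by the question, and the effect of that belief on the BPI score. The documents give neither.

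**The case against.** The strongest objection is that the sentence is indirect speech in a protocol that uses sham and active as its own labels throughout. The intensity terms in parentheses may be the words actually put to subjects. This stands as a possibility. But as the sentence is built, sham and active are the alternatives asked about and intensity is the gloss, so a site following it literally would use the label.

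Second, the consent text is not part of the public document. It may already mention a sham, in which case the question reveals little. This also stands: one cannot say that subjects are told *only* about intensity, just that both descriptions of what they are told use those terms.

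Third, subjects feel their own stimulation from the start, so some difference in expectation may exist whatever is asked. Correct: rewording removes only what the question adds.

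A reader might go further and infer that the question unblinds subjects, or that it inflates the treatment difference because sham subjects will conclude that they hold the sham. The documents support neither. No allocation is disclosed. The 84.9% figure, under 1:1 allocation, means that at least 69.8% of active subjects believed they had the sham, so a prompt heard by both arms could move active subjects too and push the difference toward zero. One could also assume a bias and convert it to a type I error, but that result would only restate the assumption.

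**Conclusion.** The point holds as a risk created by a stated procedure. As written, the plan puts a sham label on low intensity at week 6 of 12, contrary to its own framing and ahead of its own disclosure time, with a self-reported primary outcome still to be collected. The conclusion rests on two assumptions: that the item is asked in roughly the words given, and that subjects have not already been told of a sham elsewhere. If either fails, what remains is that the exact wording and order should be stated.

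Size and direction of bias: not derivable from the documents. The point should not be read as a claim that the trial's result would be biased in favour of the device, or that the earlier blinding data show failure. It is a cheap improvement and affects neither the sample size nor the analysis.

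**What to change.** Keep the guess at both 6 weeks and 3 months, and specify in the Blinding section:

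- The item uses the terms subjects were given: lower intensity, higher intensity, or don't know.
- The same item is used at both times, so that the two guesses can be compared.
- It is asked only after that visit's outcome questionnaires have been submitted.
- Any question using the words sham or active comes only after all 3-month outcomes, including QST, are complete.

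Dropping the week-6 guess is not recommended. It would lose the only planned guess from subjects who leave between week 6 and 3 months, in a trial that expects 15% dropout overall. Using one wording at week 6 and another in its place at 3 months would make the two guesses hard to compare.

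The cost is negligible: the wording and position of one item change. If the item in use is already neutral, the sponsor need only quote it and state its order.
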